4. STUDY DESIGN

4.1. Overview

This is a randomized, double-blind, placebo-controlled study in patients with moderate to severe psoriasis. The purpose of this study is to assess the clinical efficacy, safety, and PK of ESK-001 compared to placebo in patients with moderate to severe psoriasis.

Study details include:

- Overall study duration will be approximately 20 weeks.
- The treatment period will be 12 weeks.
- Study will be conducted at approximately 65 sites in North America and Europe.
- Study size is planned for a total of approximately 210 patients randomized across 6 study arms (5 assigned to ESK-001 and 1 assigned to placebo).
- Efficacy (including PASI, sPGA, QoL measures), safety, and PK will be assessed.
- Exploratory PD assessments include blood- and skin-based RNA, proteomic, and other molecular markers
- Patients completing the study will be eligible to enter an open-label extension study to receive ESK-001 long term (if all extension study entry criteria are met).

[REDACTED]

[REDACTED]

[REDACTED]

[REDACTED]

[REDACTED]

4.3. Order of Assessments

The following priority order will be in effect, if applicable, when more than one assessment is required at a predose and postdose time point, with PK blood sampling being performed nearest to the specified time:

1. 12-lead ECG
2. Vital signs
3. PROs (DLQI, EQ-5D, NRS)
4. Adverse Event and Concomitant Medication collection
5. Disease activity skin assessments (PASI, BSA, sPGA); physical examination
6. PK and PD/biomarkers blood sampling
7. Blood and urine sampling for safety assessments
8. Skin biopsy and skin tape stripping (if consent obtained)
9. Study drug administration by the site staff

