1.2. Study Schema

1.3. Schedule of Assessments

Procedure	Screening	Treatment Period (Weeks)							ET	Safety Follow-up (Weeks)	
		1	2	4	8	12	US	14		16 EOS	
Timing of Visit (Days)	-28 to -1	1	8	15	29	57	84	-	-	98	115
Visit Window (Days)	28 to -1		±1	±1	±3	±3	±3	-	-	±3	±3
Informed consent	X										
Inclusion and exclusion criteria	X	X									
Vital signs	X	X	X	X	X	X	X	X	X	X	X
Physical examination ^A	X	X	X	X	X	X	X	X	X	X	X
Medical history	X	X							X		
Pregnancy test (WOCBP only) ^B	X	X			X	X	X	X	X		X
FSH (postmenopausal women only) ^C	X										
HIV, HBV, HCV screening	X										
QuantiFERON TB test ^D	X										
Coagulation	X										
Complete blood count	X	X		X	X	X	X	X	X		X
Serum chemistry	X	X		X	X	X	X	X	X		X
Fasting lipid panel		X				X					X
Immunoglobulin levels (total)		X ^E			X	X	X				X
12-lead ECG	X	X ^E		X	X	X	X	X	X		X
Urinalysis	X	X			X		X		X		X
DNA sample ^F		X									

Procedure	Screening	Treatment Period (Weeks)							ET	Safety Follow-up (Weeks)	
			1	2	4	8	12	US		14	16 EOS
Timing of Visit (Days)	-28 to -1	1	8	15	29	57	84	-	-	98	115
Visit Window (Days)	28 to -1		±1	±1	±3	±3	±3	-	-	±3	±3
Study drug administration at site ^G		X			X	X	X				
Study drug dispensing ^H		X			X	X					
AE/con-med review	X	X	X	X	X	X	X	X	X	X	X
Disease activity skin assessments ^I	X	X	X	X	X	X	X	X	X	X	X
PRO ^J		X		X	X	X	X		X		X
PD/biomarkers		X						X			
Skin biopsy and tape stripping ^{F,K}											
Plasma biomarker profile ^L		X ^E		X	X	X	X		X		X
Blood RNA-seq profile ^M		X ^E		X	X	X	X		X		X
Blood cell-based PD biomarkers ^{N,O}		X			X	X	X			X	
T/B/NK counts		X ^E			X	X	X				X
PK blood sampling ^P		X			X	X	X		X ^Q	X	

Footnotes

EOS = end of study; ET = early termination; US = unscheduled visit

- A. Full physical examination at Screening and Day 1; abbreviated physical examination symptom driven at all other visits.
- B. Serum pregnancy test at Screening; urine pregnancy test at other indicated visits.
- C. Menopause is defined as absence of menses for 12 consecutive months.
- D. QuantiFERON TB tests should not be performed within 4 weeks of COVID-19 mRNA vaccinations or boosters. If a patients test result is indeterminate it may be retested one time. If both tests are indeterminate the patient will be considered a screen fail.
- E. Predose
- F. Optional, collected only if patient provides specific consent.

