- G. Administration of the visit day dose of study drug by the site staff. Patients should be reminded to bring their study drug with them to the clinic and take their dose when instructed by the site staff. Randomization occurs prior to first administration of study drug on Day 1.

- H. Dispense sufficient study drug to last until the next study visit
- I. Includes PASI, BSA and sPGA
- J. Patient reported outcomes (DLQI, EQ-5D and NRS)
- K. Lesional and nonlesional samples; predose on Day 1
- L. Biomarker panel, exploratory proteomics
- M. Exploratory transcriptomics
- N. To be conducted at selected study sites. Fresh blood needs to be collected and cell assays conducted on the day of collection.
- O. PD Samples for patients will be collected on Day 1 and Week 8 predose and 2 hours (± 15 min) and 4 hours (± 15 min) postdose. At Week 4 and 12 patients will take their dose in the clinic and a PD sample will be collected predose. A random sample will be taken at Week 14.
- P. PK Samples for patients will be collected on Day 1 and Week 8 predose and 30 minutes (± 5 min), 1 hour (± 5 min), 2 hours (± 15 min) and 4 hours (± 15 min) postdose in a fasted condition. Patients may have a snack between the 2- and 4-hour draw. At Week 4 and 12 patients will take their dose in the clinic and a PK sample will be collected predose. A random sample will be taken at Week 14.
- Q. Collected if the ET visit is within 14 weeks of the initiation of study drug treatment.

[figure not shown]

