6.8. Administration of Study Drug

The study site staff will administer a dose of study drug to each patient on Day 1 (first dose), and on the Week 4, 8, and 12 visit days. Patients should be clearly instructed not to take study drug on these study Days, but to bring their study drug with them to the clinic and take [REDACTED]

Study drug will be dispensed to patients as a 4-week supply at the Day 1, Week 4, and Week 8 visits.

At the Week 4, 8 and 12 study visits patients must return all study drug [REDACTED]

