8.3.4. Electrocardiograms

12-lead ECGs will be performed at time points detailed in the Schedule of Assessments (see [Section 1.3](#)).

The 12-lead ECGs will be performed after the patient has been resting supine or semi-reclined for ≥ 5 minutes. The ECG paper tracing will be assessed by the study investigator for any abnormality and for clinical significance. The ECG parameters that will be measured include but are not limited to: PR interval, QRS interval, RR interval, QT interval, and QTc.

The ECGs will be sent electronically to a central location to be analyzed and over-read. The study site should review the centrally read report as soon as possible once available. The central report findings should be compared to the local paper ECG findings reported by the site. Any difference in reported ECG findings should be reconciled by the Investigator. The study team does not require a report back from this central location to act on any findings identified on the paper ECG tracing that, in the opinion of the study investigator, are clinically significant.

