10.4.2. Laboratory Tests

Descriptive summaries of laboratory values, including changes from baseline and treatment-emergent abnormalities, will be generated. Shift tables reflecting changes from baseline (e.g., normal to low, high) will be presented for a subset of laboratory parameters.

The liver function tests, namely ALT, AST, ALP, and TBL, are used to assess possible drug-induced liver toxicity (DILI). A listing of liver function test results that meet DILI criteria will be generated.

10.4.3. 12-Lead Electrocardiogram

The RR, PR, QRS, and QT intervals will be measured and read by a central laboratory. HR will be calculated as $60 / (\text{RR} \times 1000)$ (with RR expressed in msec) and rounded to the nearest integer.

Correction for Heart Rate

Corrected QT interval (QTc) will be calculated using the manually over-read QT values. Each individual ECG QT value will be corrected for HR. The measured QT data will be corrected for HR using QTcF as per the following formulae/method (with QT, RR and QTc expressed in msec):

Fridericia's Correction:

$$QTcF = \frac{QT}{(RR / 1000)^{(1/3)}}$$

ECG Numeric Variables

HR, PR, QRS, and QTcF will be summarized using descriptive statistics. For each time point of measurement, the changes from baseline will be summarized using descriptive statistics.

Categorical Analysis

The incidence count and percentage of patients with any postdose QTcF values of >450 msec, >480 msec, and >500 msec will be tabulated. Patients with QTcF values >520 msec will be listed with corresponding baseline values, Δ QTcF, and baseline and treatment HR. The incidence count and percentage of patients with Δ QTcF increase from baseline of >30 msec and >60 msec will be tabulated.

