8.1 Adverse Events

AEs will be coded to MedDRA version 25.0. AEs will be presented by SOC and PT, unless otherwise noted, in order of descending frequency on the overall total, and multiple occurrences of the same event in the same participant will be counted only once in the tables.

The following summaries of AEs will be provided:

- Overall summary of TEAEs
- All TEAEs
- Study drug related TEAE
- TEAEs by severity
- Grade 3 or higher TEAE
- Serious TEAEs (SAEs)
- Study drug-related SAEs
- TEAE leading to treatment discontinuation
- TEAE leading to death

By-subject listings of all AEs, SAEs, TEAEs leading to treatment discontinuation, TEAE leading to death will also be provided.

8.2 12-lead Electrocardiogram

12-lead electrocardiogram (ECG) data will be measured and read by local and central laboratory, and will be summarized for all subjects in the Safety Analysis Population.

8.2.1 *ECG Numeric Variables*

HR, PR, QRS, and Fridericia-corrected QT (QTcF) interval based on central ECG read and changes from baseline will be summarized by treatment group using descriptive statistics. The change from baseline of these ECG parameters at each time point will be listed for each subject.

8.2.2 *Categorical Analysis*

The number and percentage of subjects with maximum treatment-emergent post-dose QTcF values based on central ECG read in the following mutually exclusive categories will be summarized by treatment group: > 450 msec, > 480 msec, > 500 msec, > 520 msec, and > 550 msec. The number and percentage of subjects with maximum post-dose QTcF increase from baseline of > 30 msec and > 60 msec (mutually exclusive) will be summarized by treatment group.

Clinical significance will be summarized by treatment group and overall for the local and central ECG reads separately.

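### No scheduled ECG is tied to a postdose time, and the Week 4, 8 and 12 ECGs are most likely taken at trough, so the QTcF tables could miss a concentration-related effect

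*Protocol*

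**What the plan says.** - **Order within a visit.** Protocol 4.3 applies its sequence under a condition: "The following priority order will be in effect, if applicable, when more than one assessment is required at a predose and postdose time point". The ECG is item 1, PK and PD blood sampling is item 6, and the list ends with "9. Study drug administration by the site staff".
- **Dose held until clinic.** Protocol 6.8 has site staff give the dose on Day 1 and on the Week 4, 8 and 12 visit days. Of those days it says: "Patients should be clearly instructed not to take study drug on these study Days".
- **ECG schedule.** The ECG row of the Schedule of Assessments (Protocol 1.3) has one ECG at each of Screening, Day 1, Weeks 2, 4, 8, 12 and 16, and at unscheduled and early-termination (ET) visits. Footnote E (predose) is attached to Day 1 only. Protocol 8.3.4 adds no clock time: "12-lead ECGs will be performed at time points detailed in the Schedule of Assessments".
- **PK schedule.** Footnote P reads "PK Samples for patients will be collected on Day 1 and Week 8 predose and 30 minutes" and continues with draws at 1, 2 and 4 hours. At Weeks 4 and 12 the PK sample is predose only.
- **Analysis.** Protocol 10.4.3 counts "patients with any postdose QTcF values of >450 msec", with higher cut-offs and increases from baseline. SAP 8.2.2 categorises "maximum treatment-emergent post-dose QTcF values based on central ECG read". SAP Section 5 summarises ECGs by nominal visit and leaves unscheduled ones to listings.

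**The concern.** If a drug affects QT in proportion to its plasma concentration, the effect is smallest just before a dose and largest near the peak. A schedule whose on-treatment ECGs fall mainly before the dose looks for the effect where it is hardest to see. The QTcF tables across five dose levels would then say little about peak exposure, and a reader could take a clean table as more reassuring than it is.

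At Week 8 the patient is already in clinic for four hours after a dose with timed PK draws, yet no ECG is attached to any of them. QTcF and concentration therefore cannot be paired near the peak in any planned visit.

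**Working it through.** **Step 1. Place each post-baseline ECG relative to dose.** The plan gives no figure for this, so the sections are read against each other.

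| ECG | What fixes its time relative to dose | Result |
|---|---|---|
| Week 2 | No clinic dose, no held dose, no timing rule | On drug, any time after a home dose |
| Weeks 4 and 12 | Dose held (6.8); ECG item 1, dose item 9 (4.3); only a predose PK draw | Most likely predose, at or near trough |
| Week 8 | As above, plus PK draws from predose to 4 h; no ECG attached to them | Most likely predose, at or near trough |
| Week 16 | Day 115 against Day 84 for Week 12: 115 − 84 = 31 days | Off drug |
| ET | Section 7.2: 2 weeks (±7 days) after stopping drug. Section 7.3: within 2 weeks (±7 days) of leaving the study | Mostly off drug; some may be soon after the last dose |
| Unscheduled | None | Listed only, not in the tables |

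The PK position supports the predose reading. PK sampling is item 6, and footnote P requires a predose draw at Weeks 4, 8 and 12. A site following 4.3 records the ECG before a sample that is itself predose. Scheduled ECGs tied to a postdose clock time: zero.

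**Step 2. What post-dose means in the tables.** SAP 8.2.2 joins it to treatment-emergent, and SAP Section 8 starts that period at first dose and, for completers, ends it at end of study. SAP 7.1.1 and 7.4 use the same term for PASI-75 and sPGA visits. It means after the first dose. The tables therefore pool probable trough, untimed and off-drug values.

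**Step 3. How much could be lost.** Half-life, tmax and dosing interval are not in the public text, so every input here is an assumption: one-compartment oral model at steady state, half-life 4 to 24 h, absorption rate ka 0.7 and 1.5 per hour, dosing interval τ of 24 h or 12 h. With ke = ln 2 / half-life,

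C(t) ∝ e^(−ke·t)/(1 − e^(−ke·τ)) − e^(−ka·t)/(1 − e^(−ka·τ)),

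and the trough/peak ratio is C(τ) divided by the maximum of C(t).

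Example (τ = 24 h, half-life 12 h, ka = 1.5): ke = 0.0578 and the peak is at 2.06 h. C(24) = 0.25/0.75 = 0.333. C(2.06) = 0.888/0.75 − 0.046 = 1.138. Ratio = 0.333/1.138 = 0.29.

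| Half-life | Trough/peak, once daily | Trough/peak, twice daily |
|---|---|---|
| 4 h | 0.02–0.03 | 0.18–0.25 |
| 6 h | 0.08–0.11 | 0.33–0.40 |
| 12 h | 0.29–0.33 | 0.58–0.64 |
| 24 h | 0.54–0.58 | 0.76–0.80 |

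If the effect is also linear in concentration and without delay, an assumed 10 msec effect at peak would appear at trough as 10 × ratio: about 0.2 to 5.8 msec (once daily) or 1.8 to 8.0 msec (twice daily). Widening the assumptions to half-life 4 to 48 h and tmax 1 to 4 h gives ratios of 0.02–0.75 and 0.16–0.88.

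**Step 4. Whether an existing draw is near the peak.** Under the Step 3 assumptions, concentration at 2 h is 94–100% of peak. This shows only that the existing draws can bracket a peak of this kind. The sponsor's own tmax should decide which one to use.

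**The case against.** **Predose timing at Weeks 4 to 12 is inferred.** The 4.3 list carries an if-applicable condition, and the Schedule marks the ECG predose on Day 1 only. This stands: a reader might infer that the protocol prescribes trough ECGs, and it does not. The condition does appear to be met, since several assessments share a predose time point at these visits. Nor does a missing footnote imply postdose: the plasma-biomarker and RNA-seq rows show the same Day-1-only mark. If sites may choose, the time is uncontrolled and still needs stating.

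**The tables need not understate anything.** A reader might infer that any QT effect would be understated. That requires a short enough half-life and a concentration-driven effect without delay, and the public text establishes neither. With twice-daily dosing and a 24 h half-life, trough keeps 76–80% of peak. The Week 2 ECG may also fall near a peak by chance. This stands; only 'could miss or understate' is supportable.

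**The post-dose label is not an error.** Agreed. It means after first dose, and nothing in the tables claims peak timing.

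**QT is not an objective.** No objective, endpoint or planned concentration–QTcF analysis concerns it. The cardiologist on the safety committee is linked in Protocol 2.5 to overall patient safety, including events associated with JAK inhibition, so that role does not show that the trial set out to measure QT at peak. This stands, and is why the point is an improvement and not a broken analysis.

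**Earlier data may exist.** PK and ECG results from healthy participants could lie in redacted sections. Their absence is not counted against the plan, but it means the need for peak ECGs here cannot be judged fully.

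**Conclusion.** The point holds in a limited form. Read together, Protocol 4.3, 6.8 and the Schedule leave no scheduled ECG tied to a postdose time and make trough the most likely timing at Weeks 4, 8 and 12. The QTcF tables in Protocol 10.4.3 and SAP 8.2.2 could therefore miss or understate a concentration-related effect.

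The size is undetermined. Trough is about 2–58% of peak with once-daily and 18–80% with twice-daily dosing, on the assumed one-compartment model with half-life 4 to 24 h and ka 0.7 to 1.5 per hour. Translating that into msec further assumes a linear effect without delay. The documents do not support saying that an effect exists, or that the tables are bound to understate one. What does not depend on the model is the count of zero timed postdose ECGs beside Week 8 PK draws that could support one.

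**What to change.** - **Schedule of Assessments and Protocol 4.3.** Make the single existing Week 8 ECG a postdose ECG, taken just before whichever existing Week 8 postdose PK draw is nearest the tmax the sponsor knows. State that the Week 4 and 12 ECGs are predose.
- **SAP 8.2.** Label each ECG as trough or postdose. Report the Week 8 postdose QTcF change from baseline by dose against placebo, and plot it against the paired concentration.

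**Cost.** A footnote, a sentence in 4.3 and a short addition to SAP 8.2, with no added ECG, visit or blood draw. The Week 8 trough ECG is lost, though Weeks 4 and 12 still supply two. The comparison uses a predose Day 1 baseline that is not time-matched, and a 4 h ECG could follow the snack allowed between the 2 h and 4 h draws. The placebo arm offsets both at group level, not for individual patients.

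If the sponsor prefers not to move the ECG, the minimum is to state each ECG's time relative to dose, define post-dose in both documents, and say that the tables do not assess QTcF at peak concentration.

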4.4. Study Duration

The estimated study duration for each patient is approximately 20 weeks and includes:

1. The screening period: up to 4 weeks
2. Treatment period: 12 weeks
3. Safety follow-up period: 4 weeks

4.5. Study Completion

For the entire study, study completion is defined as the last visit of the last patient for any protocol related activity (last patient, last visit). For individual patients, study completion is defined as the time of the patient's last data collection.

5. STUDY POPULATION

The study population will consist of male and female adult patients with moderate to severe psoriasis. Patients must meet all the inclusion criteria and none of the exclusion criteria.

5.1. Number of Patients

Approximately 210 patients will be enrolled in the clinical study according to the inclusion/exclusion criteria. Patients who discontinue study drug or the study early for any reason may be replaced by enrollment of another patient. The Sponsor may choose, based on the evolving data (e.g., safety) from ESK-001 studies, to enroll up to 50 additional patients.

5.2. Inclusion Criteria

Patients who meet the following criteria will be considered eligible to participate in the clinical study:

1. Able and willing to provide signed informed consent to participate in this study
2. Males or females, age 18-75 years, inclusive, at the Screening Visit
3. Total body weight >40 kg (88 lb)
4. Diagnosis of plaque psoriasis for ≥ 6 months
5. Plaques covering $\geq 10\%$ of body surface area (BSA)
6. Psoriasis area severity index (PASI) score ≥ 12 and static Physician's Global Assessment (sPGA) score ≥ 3
7. Women of childbearing potential (WOCBP) must agree to adhere to highly effective methods of contraception for the entirety of the study and for 30 days after the last dose of study drug
8. Males who are sexually active with WOCBP must agree to use highly effective methods of contraception for the entirety of the study and for 90 days after the last dose of study drug

5.3. Exclusion Criteria

Patients who meet one or more of the following criteria will be ineligible to participate in the clinical study:

1. Diagnosis of non-plaque psoriasis (guttate, inverse, pustular, erythrodermic, drug induced)
2. Diagnosis of immune-mediated conditions that are commonly associated with psoriasis (e.g., uveitis, inflammatory bowel disease) or other inflammatory skin conditions that may interfere with the study assessment
3. Patients with psoriatic arthritis who are receiving systemic (oral, SC, IM or IV) immunosuppressant medications (including corticosteroids, immunosuppressant biologics) or who has or is expected, in the opinion of the investigator, to develop unstable disease.
 - Patients who are receiving a stable therapeutic regimen for their psoriatic arthritis that does not include immunosuppressants (e.g. NSAIDs) may be included in the study

4. Pregnant, lactating, or planning to get pregnant during the study period
5. Has used topical medications/treatments that could affect psoriasis evaluation within 2 weeks of the first administration of study drug
6. Has received phototherapy or any systemic medications/treatments that could affect psoriasis evaluation within 4 weeks of Study Day 1
7. Has received any therapeutic agent targeted to: IL-12 or IL-23 within 6 months, IL-17 within 4 months, or any TNF α inhibitor(s) within 2 months of first administration of study drug
8. Is currently receiving or has received any systemic immunosuppressants or immunomodulatory drugs (e.g., methotrexate, cyclosporine) within 4 weeks of the first administration of study drug or 5 half-lives whichever is longer
9. Has received agents that modulate B cells (e.g., rituximab, ocrelizumab) within 6 months of first administration of study drug
10. Has received agents that modulate T cells (e.g., abatacept, alemtuzumab) within 3 months of first administration of study drug
11. Has received JAK inhibitors (e.g., baricitinib, tofacitinib) or TYK2 inhibitors within 4 weeks of first administration of study drug
12. History of lack of clinical response to any therapeutic agent targeted to IL-12, IL-17 or IL-23 (e.g., ustekinumab, risankizumab, secukinumab, ixekizumab) at approved doses after at least 3 months of treatment
13. History of lack of clinical response, in the Investigator's opinion, to 2 or more biologic therapies at approved doses after at least 3 months of treatment
14. Has received any investigational agent, within 30 days or 5 half-lives (whichever is longer) of any study drug or is currently enrolled in an investigational study
15. Is currently receiving proton pump inhibitors such as omeperazole or esomeprazole. It is acceptable to substitute a histamine 2 receptor blocking drug or oral antacids prior to Study Day 1
16. Patients with QTcF >450 msec (males) or >470 msec (females) at screening
17. Unstable cardiovascular disease, defined as a recent clinical deterioration (e.g., unstable angina, rapid atrial fibrillation) or a cardiac hospitalization within the last 3 months
 - Patients requiring medications to treat underlying stable chronic cardiovascular disease, including but not limited to β -blockers, should be on a stable dose for at least 4 weeks before Study Day 1
18. Active herpes viral infection, including herpes simplex 1 and 2 and herpes zoster identified on examination and/or medical history within 2 months of administration of study drug

19. Patients with hepatitis C virus (HCV), or hepatitis B virus (HBV) or human immunodeficiency virus (HIV) or active or inadequately treated latent tuberculosis (TB) infection at screening
20. Has any of the following lab abnormalities:
 - Absolute neutrophil count $<1.5 \times 10^9/L$
 - Hemoglobin $<9 \text{ g/dL}$
 - AST/ALT $\geq 2 \times \text{upper limit of normal (ULN)}$
 - Albumin $<3 \text{ g/dL}$
 - Total bilirubin $\geq 2 \times \text{ULN}$ (patients with a history of Gilbert's syndrome are not eligible)
 - Glomerular filtration rate <50 (Cockcroft and Gault method)
21. History of any immune-mediated or inflammatory medical condition for which patient requires current systemic (oral, SC, IM or IV) corticosteroids
 - Stable doses of inhaled corticosteroids for treatment of asthma are allowed
22. History of serious bacterial, fungal, or viral infections that led to hospitalization and IV antibiotic treatment within 90 days prior to screening, or any recent serious infection requiring antibiotic treatment within 30 days of Study Day 1
23. Known current malignancy or current evaluation for a potential malignancy or history of malignancy within the past 5 years prior to screening, except for adequately treated basal cell skin carcinoma, carcinoma in situ of the cervix and breast ductal carcinoma in situ
24. Live vaccines (e.g., varicella, measles, mumps, rubella, cold-attenuated intranasal influenza vaccine, and bacillus Calmette-Guérin) within 4 weeks of Study Day 1
25. Patient has a known hypersensitivity to any component of the study drug
26. Patient has planned surgery during the study period
27. Any acute or chronic illness/condition or evidence of an unstable clinical condition that in the investigator's judgement will substantially increase the risk to the patient if he or she participates in the study
28. History of mental illness within the last 5 years, unless the patient fulfills one of the following conditions:
 - Receiving a fixed regimen of psychiatric medications for at least 6 months before screening, displays no sign of acute mental illness and, in the opinion of the investigator, the patient is able and safe to participate in the study
 - Has not required or been prescribed any psychiatric medication (including but not limited to antidepressants or anxiolytics) within 12 months before screening and, in the opinion of the investigator, the patient is able and safe to participate in the study
29. Patient who, for any reason, is deemed by the investigator to be inappropriate for this study or is unable to comply with the study protocol

